2.3 Visit Schedule and Study Assessment

The flow chart of visit schedule and study assessments is given in Table 2 of the KD019-211 Protocol.

2.4 Efficacy Assessments

2.4.1 Height-Adjusted Total Kidney Volume

htTKV will be assessed by MRI at Months 12, 18, 24, and 30 days post-dose. htTKV, reported in milliliters (mL), is calculated using total kidney volume obtained from MRI divided by height in meter.

2.4.2 Estimated Glomerular Filtration Rate

eGFR will be assessed using the MDRD-4 formula as presented in Table 1. As indicated in Table 2 of the study protocol serum creatinine will be assessed at the Screening, Day 1, Day 14, Day 28, then monthly until Month 12, then every 2 months until Month 24; and 30 days from last dose.

Table 1: 4-Variable Modification of Diet in Renal Disease (MDRD-4) Formula

High Level Formula for Black or African-American Males:

 $eGFR = 175 \times (Scr^{-1.154}) \times (Age^{-0.203}) \times 1.212$

High Level Formula for Males NOT Black or African-American (any other option): $eGFR = 175 \times (Scr^{-1.154}) \times (Age^{-0.203})$

High Level Formula for Black or African-American Females:

 $eGFR = 175 \times (Scr^{-1.154}) \times (Age^{-0.203}) \times 1.212 \times 0.742$

High Level Formula for Females NOT Black or African-American (any other option):

 $eGFR = 175 \times (Scr^{-1.154}) \times (Age^{-0.203}) \times 0.742$

Note: Age is shown in years. Scr = serum creatinine

3 STATISTICAL METHODS

3.1 General Methods

3.1.1 Computing Environment

All statistical programming and data analyses will be performed using SAS® Version 9.4 on a Windows platform.

3.1.2 Sample Size Justification and power calculations:

Based on the results presented in Caroli, et.al.¹ it is anticipated that the mean change from baseline in htTKV at 12 months will be 83.6 (\pm 90.0) mL in the placebo group. Assuming the mean change from baseline in htTKV at 12 months is 26.4 mL for the tesevatinib group, 40 subjects per group would yield approximately 80% power to detect a difference between treatment groups based on a 2-sided t-test with a Type I error rate of 0.05. Ten additional subjects per group will be added (i.e., for a total of 50 subjects per group) to adjust for dropouts and differences in analysis methodologies (e.g., the htTKV data will be log-transformed).

3.2 General Considerations

General considerations for descriptive statistics and presentation for continuous and categorical data are given below.

3.2.1.1 Continuous Variables

Continuous data will be described using descriptive statistics: number of observations (n), mean, standard deviation, median, minimum, and maximum.

Means, medians, standard deviations, and confidence intervals (CIs) will be reported to one decimal place more than the data reported on the case report form (CRF) or by the vendor. Minimum and maximum will be reported to the same number of decimal places displayed on the CRF or by the vendor. P-values will be reported to 4 decimal places.

3.2.1.2 Binary Endpoint and Other Categorical Variables

For endpoints with two possible outcomes (i.e., dichotomous endpoints) such as alive/otherwise or response/otherwise within specific periods, the 95% confidence interval will be calculated with Clopper-Pearson method. For other categorical variables, the counts and percent of each category within a parameter will be

calculated for observed data only. The denominator for all percentages, unless otherwise specified, will be the number of subjects in the treatment group or in the specified analysis population.

3.2.2 Study Day

The Study Day for all assessments prior to the first study drug administration is calculated as the difference between the date of the event or measurement (e.g., adverse event [AE] onset date, assessment date, sample collection date) and the start date of study treatment. The day before the start of study treatment is Study Day -1.

The Study Day for all post-assessments after the first study drug administration is calculated as the difference between the date of the event or measurement (e.g., AE onset date, assessment date, sample collection date) and the start date of study treatment plus one day. The first day of study treatment is Study Day 1.

3.2.3 Baseline

Baseline value is defined as the valid and last non-missing value obtained within 28 days prior to subject receiving the first study medication, unless otherwise stated under the related assessment section. Baseline can be the day before the first study medication or on the same day as the first study medication if a pre-dose assessment is available. Subjects without data on a parameter before the first study medication will have a missing baseline for this parameter.

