- 13. Subject is taking any medication known to inhibit the cytochrome P450 (CYP)3A4 isozyme or any drugs that are CYP3A4 inducers, or any drugs associated with torsade de pointes or known to prolong the QTcF interval, including anti-arrhythmic medications within 2 weeks prior to screening. A stable regimen (≥ 4 weeks) of antidepressants of the selective serotonin reuptake inhibitor (SSRI) class is allowed (common SSRIs include escitalopram oxalate, citalopram, fluvoxamine, paroxetine, sertraline, and fluoxetine).
- 14. Uncontrolled intercurrent illness that would limit compliance with study requirements including, but not limited to ongoing or active infections or psychiatric illness.
- 15. Subject is pregnant, plans to become pregnant, or nursing.

16. Known to be positive for the human immunodeficiency virus or hepatitis B or C, as indicated by a positive test at screening.

- 17. Known to be immunocompromised.
- 18. Documented presence of renal vascular disease resulting in uncontrolled hypertension.
- 19. Has previously received an epithelial growth factor receptor (EGFR) inhibitor (including, but not limited to, erlotinib, gefitinib, osimertinib, afatinib, cetuximab, panitumumab, or an investigational agent).
- 20. Allergy or hypersensitivity to components of either tesevatinib, matched placebo, or their formulations.
- 21. Aphakic due to previous cataract surgery or congenital abnormality.

Note: The sponsor has the option to exclude a subject from enrollment, if, based upon the subject's medical history or screening results, it is felt that a subject's safety may be at risk and/or if the safety data may confound the study results.

Maximum duration of subject involvement in the study:

The planned duration of the screening period is no more than 28 days prior to dosing (42 days for MRI and ocular assessments). The planned duration of treatment period is approximately 730 days (or 24 months). The follow-up period will be 30 days from the last dose of study drug.

Endpoints and statistical analysis:

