Informed consent	>					
Medical and PKD history (include genotype, if available)	*					
Physical examination ^d (including weight)	~	~	~	~	~	~
Vital signs ^e	~	~	~	~	~	~
Supine 12-lead ECG ^f	~	~	~	~	~	~
Clinical laboratory tests ^g	~	~	~	~	~	~
Ocular evaluation ^h	>				•	>
Echocardiogram ⁱ	>			~	~	~
Pregnancy test ^j	>	~		~	~	~
MRI ^k	•				(every 6 months beginning at Month 12)	•
Randomization		~				
Study drug/placebo dispensed		~	~	*	~	>
Record adverse events	>	~	~	~	~	~
Record concomitant medication	>	~	~	*	•	>
Drug compliance/collection ¹		~	~	~	~	~

Abbreviations: ECG, electrocardiogram; MRI, magnetic resonance imaging; PKD, polycystic kidney disease; QTc(F), QT interval corrected for heart rate using Fridericia's formula; TSH, thyroid stimulating hormone

- a. Screening evaluations may be combined with Day 1 pre-treatment laboratory evaluations if both are done within 4 days before first dose of study drug. Screening MRI and ocular assessments may be performed up to 6 weeks prior to Day 1.
- b Follow-up treatment period visits to be performed monthly (every 28 ± 1 day). For those subjects continuing on study beyond 12 months, visits will occur every 2 months ± 3 days between Months 12 and 24.
- c. The End-of-study visit is to be performed 30 days (± 3 days) after last dose of study drug.
- d. A complete physical examination is to be done at the Screening and End-of-study visits. Height will only be measured at Screening. Symptom-driven physical examinations will be performed on Days 1, 14, 28, every 28 days from Months 2 to 12, and every 2 months from Months 12 to 24. See Section 7.5.1 for a description of the body systems and evaluations to be performed at each visit (eg, cardiac tamponade, ocular toxicity and xerostomia assessments).
- e. Vital sign measurements will include sitting blood pressure, heart rate, respiratory rate, and oral or tympanic temperature. On Day 1, measurements should be performed predose and 1 and 4 hours postdose. See Section 7.5.2 for details on vital signs measurement.

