- k. Screening MRI will be performed after informed consent form has been signed and prior to other screening assessments. Magnetic resonance imaging will be performed at Month 12, 18, and 24, and at the End-of-study visit
- 1. Subject diaries will be dispensed on Day 1 and reviewed/collected at each visit.

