2.2 Study Design

This is a Phase 2b, multicenter, double-blind, randomized, parallel group study to evaluate the change from baseline in htTKV as measured by MRI in subjects with ADPKD treated with tesevatinib or placebo. Male and female subjects with ADPKD, 18 to 60 years of age and with an eGFR ≥ 30 mL/min/1.73 m2 and ≤ 80 mL/min/1.73 m2 will be enrolled. Up to 100 male and female subjects will be randomized 1:1 to receive 50 mg of tesevatinib once daily (QD) or placebo. The study will be conducted at approximately 25-30 sites in the United States.

Subjects will be screened up to 28 days before initiation of treatment with tesevatinib or placebo (certain screening assessments may be conducted up to 42 days prior to dosing). Screening assessments will include medical and PKD history, physical examination, vital signs, electrocardiograms (ECGs), clinical laboratory evaluation (including hematology, serum chemistry, coagulation, thyroid stimulating hormone, urinalysis, and pregnancy), ocular examination, echocardiogram, and MRI. Calculation of htTKV at screening for eligibility determination may be performed by a local radiologist.

Starting on Day 1, subjects will receive 50 mg QD of tesevatinib or placebo for up to 24 months. During the Early Treatment Period (Days 1 to 28), subjects will report to

the study site on Days 1, 14, and 28; subjects will be followed every 28 days from Months 2 to 12 and every other month from Months 12 to 24. Safety assessments will be performed at regular intervals throughout the study and will include physical examinations, vital signs, ECGs, clinical laboratory evaluations, ocular examination, and echocardiograms. Magnetic resonance imaging to determine the change from baseline in htTKV will be performed at Months 12, 18, and 24. Entry into the study will be based on local MRI readings, but central MRI readings and htTKV calculation will be performed at baseline and during the study.

All subjects will undergo an end-of-study evaluation approximately 30 days after the last dose of study drug.

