3.3 Analysis Populations

The following are the set of analysis populations.

Screened Population: All subjects who sign the Informed consent form (ICF) will be included in the Screened Population.

Safety Population: The Safety Population is defined as all subjects who receive at least 1 dose of study medication. Subjects will be analyzed according to the study drug they actually received.

Intent-to-treat (ITT) Population: The ITT population is defined as all randomized subjects. Subjects will be analyzed according to the study medication to which they were randomized.

Modified Intent-to-treat (mITT) Population: The mITT Population is defined as all subjects who receive at least 1 dose of study medication. The mITT Population will be used for tables of demography and baseline characteristics. Subjects will be analyzed according to the study medication to which they were randomized.

Efficacy Population: The Efficacy Population is defined as all subjects in the mITT population who complete at least 12 months of tesevatinib or placebo treatment and have a centrally read MRI at baseline and after 12 months of treatment. Subjects will be analyzed according to the study drug they actually received. This will be the primary population for efficacy analyses.

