3.9.3 Secondary Endpoint Analyses: Change from Baseline in eGFR

A secondary endpoint is the change from baseline in eGFR at months 12, 18, 24, and 30 days post-dose using the MDRD-4 formula (see Table 1).

For the 30 days post-dose endpoint, the change in eGFR from baseline to posttreatment follow-up is annualized (divided) by each subjects' treatment duration (in years). This normalization is necessary, otherwise the treatment group having more dropouts or earlier dropouts may bias the results.

At each timepoint (ie, months 12, 18, 24, and 30 days post-dose) and analysis of covariance (ANCOVA) model will be used to evaluate treatment effect. The ANCOVA model has eGFR as the dependent variable, treatment group as the factor, and baseline eGFR, patient age, and baseline htTKV as covariates.

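### The SAP's 28-day baseline window is shorter than the 42 days the protocol allows for the only pre-dose MRI, so the rule as written can drop compliant subjects from the primary analysis

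*SAP*

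**What the plan says.** SAP 3.2.3 gives one general definition: "Baseline value is defined as the valid and last non-missing value obtained within 28 days prior to subject receiving the first study medication". It yields only where the section on the assessment concerned says otherwise. The same paragraph ends: "Subjects without data on a parameter before the first study medication will have a missing baseline for this parameter".

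The protocol gives MRI a longer window. Table 2, footnote a: "Screening MRI and ocular assessments may be performed up to 6 weeks prior to Day 1". The synopsis gives the same 42 days under the maximum duration of involvement. Footnote k adds: "Screening MRI will be performed after informed consent form has been signed and prior to other screening assessments". SAP 2.2 repeats in its design summary that "certain screening assessments may be conducted up to 42 days prior to dosing", without naming MRI or defining baseline.

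The Efficacy Population in SAP 3.3, the primary set for efficacy, requires subjects to "have a centrally read MRI at baseline and after 12 months of treatment". The primary ANCOVA in SAP 3.9.2 uses log10 baseline htTKV both as covariate and within the change score.

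**The concern.** A scan taken five or six weeks before Day 1 complies with the protocol but falls outside the SAP's baseline window. Table 2 schedules no later pre-dose MRI to take its place. Laboratory tests and ECGs are repeated on Day 1, so a 28-day limit does them no harm; htTKV has one pre-dose value.

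Membership of the primary analysis set then depends on which sentence of SAP 3.2.3 the programmer follows. The 28-day sentence leaves the subject without a baseline. The closing sentence calls baseline missing only when there are no pre-dose data, which suggests the scan counts. Two programmers could build different primary sets from the same database.

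**Working it through.** **1. The windows.** SAP 3.2.3 allows 28 days and the protocol allows 42 days for MRI. The gap is 42 - 28 = 14 days, Days -42 to -29, or 14/42 = one third of the permitted window. This says nothing about the share of subjects scanned in that period.

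**2. Is an exception stated?** The SAP sections that deal with htTKV are 2.4.1 (assessment), 3.9.1 (log transformation), 3.9.2 (primary analysis) and 3.10.1 (longitudinal analysis). None gives a baseline window.

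**3. Is there a substitute scan?** Table 2 schedules MRI at Screening, at Months 12, 18 and 24, and at End of Study. The screening MRI is also placed ahead of the other screening assessments, so early scans are plausible.

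**4. What depends on baseline htTKV?**
- The Efficacy Population and the primary ANCOVA, as described above.
- The mITT repeat and the Month 18, 24 and 30-days-post-dose htTKV ANCOVAs (SAP 3.10), which need the same baseline. SAP 3.2.4 says missing data are in general not imputed, so the mITT repeat does not recover the subject.
- The eGFR ANCOVA (SAP 3.9.3), whose terms are "treatment group as the factor, and baseline eGFR, patient age, and baseline htTKV as covariates".
- The longitudinal htTKV model could keep the subject's later values, but its time variable runs from baseline, so it too needs a settled baseline date.

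**5. The plan's own power figure.** Inputs from SAP 3.1.2 and Protocol 9.12: mean changes 83.6 and 26.4 mL, SD 90.0 mL (given for placebo, taken as common to both arms), two-sided alpha 0.05, 40 per arm.

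Difference = 83.6 - 26.4 = 57.2 mL. For a two-sample t-test with n per arm, the noncentrality is 57.2 / (90 × √(2/n)) on 2n - 2 degrees of freedom. At n = 40 it is 57.2 / 20.12 = 2.84 on 78 df, and power is 80.2%. This reproduces the stated figure of about 80%.

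**6. Illustrated loss.** The shares below are assumptions, applied equally to both arms. The starting value of 40 per arm is a floor, because the protocol expects at least 40 of 50 per arm to complete all procedures, which is more than reaching Month 12. The starting value of 45 assumes 10% dropout from 50 by Month 12.

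| Share of scans on Days -42 to -29 | From 40 per arm: n, power | From 45 per arm: n, power | SE inflation, 1/√(1 - share) |
|---|---|---|---|
| 0% | 40, 80.2% | 45, 84.7% | 1.000 |
| 5% | 38, 78.1% | not computed | 1.026 |
| 10% | 36, 75.8% | 40, 80.2% | 1.054 |
| 20% | 32, 70.6% | 36, 75.8% | 1.118 |

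(45 × 0.9 = 40.5 is rounded down to 40.) The power figures use the planning t-test in mL, while the primary analysis is a log10 ANCOVA. The standard-error factor holds approximately on either scale.

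**7. Bias.** Table 2 places randomization on Day 1, after the screening MRI. Scan timing cannot depend on the assigned arm, so the exclusion would cost precision without introducing a treatment-related bias.

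**The case against.** The strongest reply is that nobody would read the SAP this way. The Efficacy Population definition does not mention 28 days, and Protocol 9.5 defines the same set with no such limit. With only one scheduled pre-dose MRI, the natural meaning of an MRI at baseline is the screening scan. SAP 2.3 refers to protocol Table 2 for the visit schedule, and footnote a of that table carries the six-week allowance. SAP 2.2 repeats the 42 days, and the closing sentence of 3.2.3 points the same way. On size, the shares are assumed, and with 45 per arm a 10% loss still leaves 80.2% power.

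Most of this stands. Use of the screening MRI is the likely intent, the number affected may be zero, and the power figures are illustrative only. But SAP 3.2.3 requires an exception to be stated under the related assessment section, and none of these places states one for htTKV. Followed exactly, the rule still removes compliant subjects.

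**Conclusion.** The concern holds. The baseline rule in SAP 3.2.3 is wrong as written for htTKV: it excludes scans that the protocol permits, and no section supplies the exception. This is clear from the documents alone.

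The effect is conditional. It needs some scans on Days -42 to -29 and a programmer who applies the 28-day sentence literally; the documents establish neither. If both occur, standard errors rise by about 2.6%, 5.4% and 11.8% at assumed shares of 5%, 10% and 20%. At the planned 40 per arm, power by the planning t-test falls from 80.2% to 78.1%, 75.8% and 70.6%. Because the rule decides who enters the primary analysis and is easily corrected, it should be settled before unblinding.

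**What to change.** Add to SAP 3.2.3 or 2.4.1, before unblinding, that the htTKV baseline is the last centrally read MRI on or before first dose, within the protocol's 42-day screening window. Keep 28 days as the general rule for other parameters. Reword the closing sentence of 3.2.3 to agree, and state how a scan older than 42 days is treated, so that the same conflict does not recur at the new limit.

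The protocol gives ocular assessments the same 42 days. The SAP plans no ocular analysis, so extending the wording to them would be for consistency only.

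The cost is a few lines of SAP text, with no new data collection, no protocol amendment and no change to the sample size.

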6.7.1.2. Response to QTcF Interval Prolongation

The following guidelines should be used in the management of QTcF prolongation. Subjects will have ECGs performed as outlined in Table 2. If the average QTcF interval (from 3 consecutive ECGs taken with an interval of at least 1-2 minutes within 30 minutes) increases to > 60 msec above the highest average predose value (average of Day 1 predose and screening values) or to the level of ≥ 480 msec according to local site analysis:

- Hold study drug until central read is confirmed.
- Check electrolytes, especially magnesium and potassium; correct abnormalities as clinically indicated.
- Manage as clinically indicated with cardiology consultation as needed.
- Contact the Medical Monitor to discuss additional monitoring.

If results are confirmed by the central reader, the subject may be removed from the study after discussion with the Medical Monitor. If the subject continues in the study, appropriate management and ECG follow-up should be discussed with the Medical Monitor.

Elevated Amylase

If subjects develop an elevated serum amylase during the study that is $> 2.0 \times ULN$, then additional evaluations should be performed. These should include evaluating serum lipase, amylase isoenzymes, and fasting triglycerides as well as obtaining history regarding symptoms of pancreatitis, symptoms of dry mouth, and use of alcohol. The subject should have a drug holiday for 28 days, with amylase measured at the end of the drug holiday. If the amylase is back to the baseline value after the end of the drug holiday, study drug may be restarted, and amylase measured approximately 14 days later, and then at the start of each cycle of study drug administration. If results continue to be abnormal, the subject will be removed from study. If an elevated serum amylase that is $> 2.0 \times ULN$ occurs a second time, the subject will be removed from the study.

Elevated Creatinine Phosphokinase

If subjects develop an elevated serum CPK during the study that is $> 2.0 \times$ ULN, additional evaluations should be performed. These should include evaluating serum CPK isoenzymes as well as obtaining history regarding muscle-related symptoms or strenuous or prolonged exercise.

Pulmonary Toxicity

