The Investigator should assess out-of-range clinical laboratory values for clinical significance, indicating if the value(s) is/are not clinically significant or clinically significant.

Abnormalities in clinical laboratory tests that lead to a change in subject management (eg, dose delay, requirement for additional medication or monitoring) are considered clinically significant for the purposes of this study, and will be recorded on the AE eCRF page.

Abnormal clinical laboratory values, which are unexpected or not explained by the subject's clinical condition may be, at the discretion of the Investigator or Sponsor, repeated until confirmed, explained, or resolved as soon as possible. If laboratory values constitute part of an event that meets criteria defining it as serious, the event (and associated laboratory values) must be reported as an SAE (see Section 8.2.3).

At the investigator's discretion, any subset of the laboratory panels in Table 6 may be duplicated in local laboratories for an immediate medical assessment. However, inclusion and

exclusion criteria as well as the final statistical analysis will be based on results from the central laboratory.

Table 6: Clinical Laboratory Tests

	Serum Chemistry		
• albumin	• BUN	 phosphorous 	
 amylase 	• calcium	• potassium	
 alkaline phosphatase 	• chloride	random glucose	
• ALT	• creatinine	• sodium	
• AST	CPK (plus CPK isoenzymes	total & direct bilirubin	
• bicarbonate	if CPK is elevated)	• total protein	
	 lactate dehydrogenase 	• magnesium	
	Hematology		
RBC count	hemoglobin	• MCV	
WBC with differential	hematocrit	• MCH	
(including neutrophils,	platelet count	• MCHC	
basophils, eosinophils, lymphocytes, monocytes)			
Tymphocytes, monocytes)			
	Coagulation	Г	
• PT	• PTT	• INR	
	Urinalysis		
• appearance	• leukocytes	occult blood (microscopic	
• color	• protein	examination of sediment	
• pH	• glucose	will be performed only if the results of the urinalysis	
 specific gravity 	bilirubin	dipstick evaluation are	
• ketones	 urobilinogen 	positive)	
Other			
Creatinine clearance ^a	• cystatin C	• TSH	
• Pregnancy test ^b	• fasting triglycerides ^c	Hepatitis and HIV ^f	
•	• lipase ^d	• HbA1c ^f	
	• amylase isoenzymes ^e		
	• CPK isoenzymes ^f		

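### Baseline eGFR is a single pre-dose creatinine although two are scheduled; averaging them would sharpen the secondary eGFR ANCOVA, by an amount that the documents do not fix

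*SAP*

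**What the plan says.** The general rule in SAP 3.2.3 is: "Baseline value is defined as the valid and last non-missing value obtained within 28 days prior to subject receiving the first study medication". It allows an exception where the section on a given assessment states one. SAP 3.9.3 states none for eGFR; it specifies the model as follows: "The ANCOVA model has eGFR as the dependent variable, treatment group as the factor, and baseline eGFR, patient age, and baseline htTKV as covariates".

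Two pre-dose creatinine draws are scheduled. SAP 2.4.2 lists them: "serum creatinine will be assessed at the Screening, Day 1, Day 14, Day 28, then monthly until Month 12". Footnote a of Table 2 in the protocol treats the Day 1 laboratory tests as pre-treatment, and general screening assessments fall within 28 days of first dose (protocol 7.1), so both values lie inside the SAP's window. Both come from one source, since protocol 7.5 says that "exclusion criteria as well as the final statistical analysis will be based on results from the central laboratory".

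The second value is not guaranteed for every subject. The same footnote says: "Screening evaluations may be combined with Day 1 pre-treatment laboratory evaluations if both are done within 4 days before first dose of study drug".

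**The concern.** A single creatinine-based eGFR carries visit-to-visit noise. In an ANCOVA, noise in the baseline covariate weakens its correlation with follow-up and leaves more residual variance. The Screening value is collected, comes from the central laboratory and lies inside the window, but the last-value rule discards it whenever a Day 1 value exists.

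Change in eGFR is a named secondary objective and the only measure of kidney function among the efficacy endpoints. The protocol synopsis expects about 40 completers per group, and no power is given for eGFR. Early on-treatment draws cannot steady the baseline, because the protocol's background section reports a median creatinine rise of 10% at Day 28 on 50 mg without a rise in cystatin C. The pre-dose values are the only ones free of that effect. What is at stake is the width of the eGFR confidence intervals.

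**Working it through.** **The plan's own figure.** The documents give no SD, correlation or power for eGFR. Their only power statement is for htTKV: difference 83.6 - 26.4 = 57.2 mL, SD 90 mL, 40 per group, two-sided 0.05. This gives 80.2% with the t distribution (78 df) and 81.1% by normal approximation, against the stated approximately 80%. It reproduces, and nothing below changes it.

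**Model for eGFR.** Let vT be the variance of true baseline eGFR between subjects, vC the variance of true change, s² the visit-to-visit variance of one eGFR, and k the number of pre-dose values averaged. Then

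residual variance V(k) = vT + vC + s² - vT² / (vT + s²/k).

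**Inputs, all assumed:** mean eGFR 55 mL/min/1.73 m²; between-subject SD 12-18; visit CV 4-8%; SD of true 12-month change 2-4; two distinct draws for everyone.

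**Worked example** (SD 15, CV 6%, change SD 3): vT = 225, vC = 9, s² = (0.06 × 55)² = 10.89.
- k = 1: 244.89 - 225²/235.89 = 244.89 - 214.61 = 30.3
- k = 2: 244.89 - 225²/230.445 = 244.89 - 219.68 = 25.2
- reduction: 1 - 25.2/30.3 = 17%

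**Month 12 range.** The smallest cut is 9.0% (SD 12, CV 4%, change SD 4) and the largest 21.3% (SD 18, CV 8%, change SD 2). A cut of 9-21% makes the standard error 1 - √0.91 = 4.6% to 1 - √0.79 = 11.1% smaller. It equals 1/0.91 - 1 = 10% to 1/0.79 - 1 = 27% more subjects. A comparison that happened to have 80% power would reach about 84-88%.

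**Later visits.** True change may vary more by Months 18-24. With SD 15 and CV 6%, the cut is 8.9% at a change SD of 6 and 5.9% at 8. Over between-subject SD 12-18 and CV 4-8%, it is 5-12% at 6 and 3-9% at 8. The values 6 and 8 are also assumptions.

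**Combined draws.** If a share f of subjects has two values, the cut is roughly f times the full figure. At f = 0.5, 9-21% becomes about 4.5-10.5%.

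**Check with correlations.** With ρ the baseline-to-follow-up correlation and r the correlation between the two pre-dose values, the proportional cut is ρ²(1 - r) / [(1 + r)(1 - ρ²)].

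| ρ | r | cut |
|---|---|---|
| 0.60 | 0.97 | 0.9% |
| 0.80 | 0.95 | 4.6% |
| 0.80 | 0.90 | 9.4% |
| 0.85 | 0.85 | 21.1% |
| 0.90 | 0.90 | 22.4% |

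The wider range is therefore about 1-22%. Age and baseline htTKV, already in the model, trim it slightly: if they explain 20-40% of the stable eGFR component, 9.4% becomes 9.1-8.6% and 21.1% becomes 20.3-19.0%.

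**Where the formula does not apply.** SAP 3.9.3 divides the 30-day post-dose change by each subject's treatment duration, which is a different outcome. In SAP 3.10.2 the baseline is a response in a random-slope model, not a covariate.

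**The case against.** The strongest reply is that this is a preference. The last-value rule is explicit, can be programmed as written, and treats both arms alike. A reader might infer from the discarded value that the eGFR comparison is biased or the SAP wrong. The documents do not support that: there is no contradiction, no Type I error problem and no bias in the randomised contrast. This part of the reply stands.

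A reader might also take 9-21% as a property of this trial, or apply it to all four eGFR time points. Neither is supported. Every input is assumed, the range belongs to the Month 12 ANCOVA with two draws each, and the later, annualised and slope analyses behave differently, as shown above.

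The protocol's QTcF rule, which refers to the "average of Day 1 predose and screening values", is weak precedent. It is a trigger for managing individual subjects, and SAP 3.13.4 does not adopt it for ECG change from baseline. It shows only that pooling these two visits is familiar to this protocol.

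Materiality is modest. The eGFR endpoints are unpowered and uncontrolled for multiplicity (SAP 3.12). The creatinine effect also limits what a tighter interval can say: a 10% rise gives 1.10^(-1.154) = 0.896 through MDRD-4, an apparent fall of about 5.7 at an assumed eGFR of 55.

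Last, changing only 3.9.3 would leave a second GFR baseline in the laboratory summaries of 3.13.2. That is a fair point, and the fix covers it. Nothing in the reply shows that averaging does harm; under the stated model it never increases the variance.

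**Conclusion.** The point holds as a low-cost gain in precision for the secondary eGFR ANCOVA. The primary htTKV analysis and the sample size are untouched.

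At Month 12 the residual variance falls by about 9-21% (standard error about 5-11% smaller) if mean eGFR is 55, between-subject SD 12-18, visit CV 4-8%, SD of true change 2-4, and every subject has two draws. None of these values is in the documents. The gain is plausibly 3-12% if true change varies more by Months 18-24, about half as large if half the subjects had combined draws, and about 1-22% over wider assumed correlations. No figure is claimed for the annualised 30-day post-dose endpoint or the 3.10.2 slope model.

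**What to change.** Before unblinding, amend the SAP in three places.

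- **3.9.3:** Baseline eGFR is the mean of the valid Screening and Day 1 pre-dose central-laboratory eGFR values within 28 days before first dose when both exist, otherwise the single value. Use it as the covariate and for change from baseline.
- **3.13.2:** Use the same definition for the GFR change summaries, so that the report has one eGFR baseline.
- **3.10.2:** State which pre-dose value or values enter the slope model as responses.

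No visit or sample is added. The cost is a few sentences and some programming, an eGFR-specific baseline that departs from the general rule (which 3.2.3 allows), and a baseline built from one value in some subjects and two in others.
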